7.5.3 Postoperative Month 4 ± 7 days (Visit 6) - All Participants

Can be obtained via medical visit, telephone contact or postal correspondence:

- Review ECOG performance score
- Assess participants for their individual pain level Numeric Pain Rating Scale
- Record disease status
- Collect all AEs (assess using CTCAE V5.0)
- Record hospitalisations
- Collect all SAEs
- Update new medications since their last visit
- Blood collection for interventional treatment participants (translational studies)
- Serial high-resolution groin ultrasound (interventional treatment)

7.5.4 Postoperative Month 6 ± 7 days (Visit 7) - All Participants

Can be obtained via medical visit, telephone contact or postal correspondence:

- Review ECOG performance score
- Provide participant with Questionnaire booklet to collect PROMS, HRQL and lymphoedema

- Lymphoedema assessments via BIS, leg circumference measurements (participating sites only) and/or Self-Report Questionnaire
- Assess participants for their individual pain level Numeric Pain Rating Scale
- Record disease status
- Collect all AEs (assess using CTCAE V5.0)
- Record hospitalisations
- Collect all SAEs
- Update new medications since their last visit
- Blood collection for interventional treatment participants (translational studies)
- Weight if available
- Record FBC, Urea and Electrolytes and LFT's if available
- Evaluate symptoms and conduct a physical examination in alignment with ESMO guidelines (interventional treatment)
- Serial high-resolution groin ultrasound (interventional treatment)

7.5.5 Postoperative Month 8 ± 7 days (Visit 8) - All Participants

Can be obtained via **medical visit, telephone contact** or **postal correspondence**:

- Review ECOG performance score
- Assess participants for their individual pain level Numeric Pain Rating Scale
- Record disease status
- Collect all AEs (assess using CTCAE V5.0)
- Record hospitalisations
- Update new medications since their last visit
- Blood collection for interventional treatment participants (translational studies)
- Serial high-resolution groin ultrasound (interventional treatment)

7.5.6. Postoperative Month 9 ± 7 days (Visit 9) - Interventional Arm

Evaluate symptoms and conduct a physical examination in alignment with ESMO guidelines (interventional treatment).

7.5.7 Postoperative Month 10 ± 7 days (Visit 10) - All Participants

Can be obtained via medical visit, telephone contact or postal correspondence:

- Review ECOG performance score
- Assess participants for their individual pain level Numeric Pain Rating Scale
- Record disease status
- Collect all AEs (assess using CTCAE V5.0)
- Record hospitalisations
- Update new medications since their last visit
- Blood collection for interventional treatment participants (translational studies)
- Serial high-resolution groin ultrasound (interventional treatment)

7.5.8 Postoperative Month 12 ± 7 days (Visit 11) - All Participants

Can be obtained via medical visit, telephone contact or postal correspondence:

- Provide participant with Questionnaire booklet to collect PROMS, HRQL and lymphoedema

- Lymphoedema assessments via BIS, leg circumference measurements (participating sites only) and/or Self-Report Questionnaire
- Review ECOG performance score
- Collect Fear of Recurrence (FoR)
- Weight if available
- Assess participants for their individual pain level Numeric Pain Rating Scale
- Record FBC, Urea and Electrolytes and LFT's if available
- Evaluate symptoms and conduct a physical examination in alignment with ESMO guidelines (interventional treatment)
- Record disease status
- Collect all AEs (assess using CTCAE V5.0)
- Record hospitalisations
- Update new medications since their last visit
- Blood collection for interventional treatment participants (translational studies)
- Serial high-resolution groin ultrasound (interventional treatment)

8. Patient Reported Outcomes (PROMS) and Health Related Quality of Life (HRQL)

PROMs are questionnaires that all participants complete at baseline, 8 weeks, 6 months, and 12 months post-surgery. In Australia, PROMs are an emerging method of assessing the quality of health care. They ask for the patient's assessment of how health services and interventions have, over time, affected their quality of life, daily functioning, symptom severity, and other dimensions of health which only patients can know. PROMs promise to fill a vital gap in our knowledge about outcomes and about whether healthcare interventions can a difference to people's lives [35, 36].

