| Study Objectives | 
Primary objective:
 
 To determine the incidence of palpable, fixed to skin and histologically positive groin nodes at 12 months in women with vulvar cancer randomised to serial high-resolution groin USM versus standard surgical groin LND 
Secondary objectives:
 
 Compare Patient Reported Outcomes (PROMS) and Health-Related Quality of Life (HRQL) between the groups Compare pain and adverse events (morbidity) between the groups Compare lower limb lymphoedema between the groups Compare cost and cost effectiveness between the groups Determine the diagnostic accuracy of pre-operative, standardised high-resolution groin ultrasound to identify groin node metastasis. 
Translational research objective:
 
 To assess the role of blood and tissue molecular biomarkers to accurately determine the burden of disease (positive lymph nodes) in vulvar cancer, assist with risk stratification and aid disease surveillance |
| Study Endpoints | 
Primary endpoint:
 
 Incidence of clinically palpable, fixed to skin and histologically positive groin lymph nodes (node metastasis) at 12 months after surgical excision of the primary vulvar tumour |

| | |

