5.5 Primary Endpoint

Incidence of enlarged clinically palpable groin nodes (groin metastasis) in women randomised to serial high-resolution groin USM compared to surgical groin LND 12 months after surgery.

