7.5 Follow-Up (Visits 4-9)

All enrolled participants, irrespective of treatment group will be followed-up for 12 months. Participants without groin LND will be provided with medical imaging request forms to receive groin ultrasound examinations every 2 months. **Changes in ultrasound patterns from “normal” to “suspicious” will alert the gynae-oncologist and trigger further clinical action, such as groin LND and histological assessment of the groin nodes. Groin USM will not be offered to women who had a groin LND (IFL or SNB) as it is not standard practice for these patients.** If ultrasound scan surveillance following sentinel node biopsy is included in the standard care protocol at any of the study sites, participants randomised to lymph node dissection (LND) can undergo ultrasound scans as part of their standard care, though it is not mandatory for this study.

Participants will be assessed for local, regional, or distant recurrence, quality of life status, and treatment morbidity for 12 months. Data collected will include documentation of the status of disease, AEs, pain level, health status, quality of life and lymphoedema.

Participants randomised to serial groin USM will be seen every 3 months by a gynaecological oncologist or gynaecologist for clinical examination as per routine standard. Participants receiving standard groin LND (either SNB or LND) will be seen at 8 weeks, 3, 6, 9 and 12 months as per standard clinical practice. Follow up will be handed over to the treating gynaecological oncologist after 12 months.

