11.2.9 Disease-Free and Overall Survival (DFS, OS)

Participants will be followed for 12 months and assessed for local, regional, or distant recurrence. Participants will be seen every 3 to 6 months. Clinical assessments will be performed at each visit. Clinical assessment, radiological work-up ± histological confirmation of recurrence will prove the presence of recurrent disease.

DFS is defined as time until the first recurrence or death from any cause. In patients without recurrence, or lost to follow-up, DFS will be censored on the date of the last follow-up visit. DFS will be compared between treatment arms using methods for the analysis of censored data. Variables to be evaluated for effect on DFS will include clinical management group (groin LND, ultrasound groin surveillance), age, medical comorbidities.

12 Trial Monitoring and Oversight

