| | SCREENING/ ELIGIBILITY | T0 BASELINE | T1 WEEK8 | T2 FOLLOW UP (MONTH 3) | T3 FOLLOW UP (MONTH 4) | T4 FOLLOW UP (MONTH 6) | T5 FOLLOW UP (MONTH 8) | T6 FOLLOW UP (MONTH 9) | T7 FOLLOW UP (MONTH 10) | T8 FOLLOW UP (MONTH 12) |
|------------------------------------------------------------------------------------------------------------------------------------------|----------------------------|----------------|-------------|------------------------------|------------------------------|------------------------------|------------------------------|------------------------------|-------------------------------|-------------------------------|
| a) US Suspicious/ Indeterminate: SNB/IFL | | x | | | | | | | | |
| b) Negative Groin Ultrasound: Randomisation To Upfront Groin LND OR 2 Monthly Groin USM + 3 Monthly Physical Examination | | x | | | | | | | | |
| Surgical Excision of The Primary Tumour - Planned Surgery | | x | | | | | | | | |
| Central Histopathology Review | | x | | | | | | | | |
| Groin USM (Interventional Treatment) | | | x | | x | x | x | | x | x |
| Current Medications | | x | x | | x | x | x | | x | x |
| Adverse Events | | | x | | x | x | x | | x | x |
| Hospitalisations | | | x | | x | x | x | | x | x |
| Serious Adverse Events | | | x | | x | x | | | | |
| Physical Examination (Interventional Treatment) | | | x | x | | x | | x | | x |
| Disease Status | | | x | | x | x | x | | x | x |
| PROMS & HRQL | FACT-V | | x | x | | x | | | | x |
| | EuroQol-5D (EQ-5D) | | x | x | | x | | | | x |
| | Lymphoedema Assessment | | x | x | | x | | | | x |
| | Fear of Recurrence (FCR-4) | | | | | | | | | x |

17. References

1. Kim, C.H., et al., *Pathologic ultrastaging improves micrometastasis detection in sentinel lymph nodes during endometrial cancer staging*. *Int J Gynecol Cancer*, 2013. 23(5): p. 964-70.
2. *Vulvar cancer statistics*. 2022 [cited 2023; Available from: <https://www.canceraustralia.gov.au/cancer-types/vulval-cancer/statistics>].
3. *6 National Health Priority Areas (The Burden of Disease and Injury in Australia)*. [cited 2023; Available from: <https://www.aihw.gov.au/getmedia/78bc02fd-a75e-4f25-a0ae-b27f7bb2a4b2/bdia-c06.pdf.aspx>].
4. NF, H. and E. PJ, *Vulvar Cancer*. Practical Gynecologic Oncology. 2021: Walters Kluwer.
5. Hoskins, W.J., *Principles and Practice of Gynecologic Oncology*. 2005: Lippincott Williams & Wilkins.

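### The protocol contradicts itself on how the palpation-based primary endpoint is ascertained in the LND arm, so groin status may not be measured alike in the two randomised arms

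*Protocol*

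**What the plan says.** The synopsis defines the primary endpoint as "Incidence of clinically palpable, fixed to skin and histologically positive groin lymph nodes (node metastasis) at 12 months after surgical excision". Section 5.5 words it more loosely, as "Incidence of enlarged clinically palpable groin nodes (groin metastasis) in women randomised to serial high-resolution groin USM compared to surgical groin LND". Both versions need someone to palpate the groin.

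Three places provide for LND women to be seen or examined:
- Section 7.5 says they "will be seen at 8 weeks, 3, 6, 9 and 12 months as per standard clinical practice".
- Section 7.5.1 (week 8, all participants) lists a physical examination with no arm label.
- Section 11.2.9 says "Participants will be seen every 3 to 6 months", with clinical assessment at each visit.

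The operational sections read differently:
- Section 7.5.2 (month 3) is headed as an interventional-arm visit. So is month 9: "7.5.6. Postoperative Month 9 ± 7 days (Visit 9) - Interventional Arm".
- Sections 7.5.4 and 7.5.8 (months 6 and 12, all participants) restrict the examination item by label: "Evaluate symptoms and conduct a physical examination in alignment with ESMO guidelines (interventional treatment").
- The section 16 schedule has one examination row, "Physical Examination (Interventional Treatment"), marked at week 8 and months 3, 6, 9 and 12.
- Section 7.5.2 describes upload and central verification of the examination report for the interventional arm only.
- Section 7.5.8 places the month-12 items, including disease status, under "Can be obtained via medical visit, telephone contact or postal correspondence". The same heading stands over week 8 and months 4, 6, 8 and 10.

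**The concern.** A palpable node cannot be established by telephone or post. A site working from the visit lists and the schedule would examine ultrasound-arm women at five set times and verify that it had done so. For an LND woman it would have no examination item from month 3 on, and could complete her month-12 disease status remotely. A site working from section 7.5 would see her in person at the same five times. Both sites would be following the protocol.

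This matters because the protocol intends a comparison between arms. Section 5.1 asks whether incidence is comparable, section 5.5 sets one arm against the other, and section 11.2.1 estimates a proportion per group and their difference. Section 11.2.9 compares DFS between arms, and the decision aid in section 8.5 needs a palpable-node probability for each option. If ascertainment differs by arm, these quantities mix the effect of management with the effect of how the groin was assessed. An examination result that was never recorded cannot be recovered at analysis.

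**Working it through.** **1. The plan's own figures, and whether this point touches them.** Section 11.1 gives stopping boundaries of 5/40, 6/60, 7/80, 9/100 and 10/120. At a true 3% it states a probability of 0.85 of declaring safety at N=120 and less than 2% of wrongly stopping. The exact prior is not stated. Assuming Beta(1.5, 31.5), which is Beta(0.5, 0.5) updated with the pilot's 1/32:
- Stopping when P(p > 0.06) > 0.70 gives exactly the five stated boundaries.
- Declaring safety when P(p < 0.06) ≥ 0.80 at N=120 means 5 or fewer events, and P(X ≤ 5 | 120, 0.03) = 0.847.
- Wrongful stopping is 1.7% over the looks at 40 to 100, and 1.8% including 120.

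The stated figures reproduce. All of them depend on ultrasound-arm events alone, so LND-arm ascertainment does not enter them.

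**2. LND-arm examination, section against section.**

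| Time | For LND examination or attendance | Against |
|---|---|---|
| Week 8 | 7.5 (seen); 7.5.1 (examination, no arm label) | 16 (row labelled interventional); telephone/post heading in 7.5.1 |
| Month 3 | 7.5 (seen) | 7.5.2 (interventional-arm visit); 16 |
| Month 6 | 7.5 (seen) | 7.5.4 (examination item interventional only; telephone/post heading); 16 |
| Month 9 | 7.5 (seen) | 7.5.6 (interventional-arm visit); 16 |
| Month 12 | 7.5 (seen) | 7.5.8 (examination item interventional only; telephone/post heading); 16 |

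Section 11.2.9 does not settle it. Visits every 3 to 6 months over 12 months allow 12/6 = 2 to 12/3 = 4 visits, against five in section 7.5. At month 9 the only mark in the section 16 schedule is the interventional examination, so the LND attendance that section 7.5 describes has no data-collection slot there.

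**3. Size if LND events are missed.** Inputs: 60 LND women (synopsis and section 6.4) and an event rate of up to 3% (section 11.1).
- Expected LND events: 60 × 0.03 = 1.8.
- Effect of one missed event: 1/60 = 1.7 percentage points.

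The protocol gives no detection rate, so d below is an assumed range. Expected events found = 1.8 × d. Probability of observing none = (1 − 0.03d)^60. With a true 3% in both arms and full detection under ultrasound monitoring, the spurious difference (ultrasound minus LND) = 0.03 − 0.03d.

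| Assumed d | Expected LND events found | P(no LND event observed) | Spurious difference (points) |
|---|---|---|---|
| 100% | 1.8 | 16% | 0 |
| 75% | 1.35 | 26% | 0.75 |
| 50% | 0.9 | 40% | 1.5 |
| 25% | 0.45 | 64% | 2.25 |

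Any such bias runs against ultrasound monitoring.

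**The case against.** The strongest case on the other side is that LND women are followed. The five attendance times in section 7.5 match the ultrasound arm's examination times in section 16. Section 7.5 also has all participants assessed for local, regional or distant recurrence, disease status is recorded for everyone, and section 12.1 says palpable groin metastases are monitored in all three groups. The telephone/post heading covers both arms and also stands over ultrasound and blood collection, so it may be meant only for items that can be done remotely. The synopsis endpoint needs histology and describes advanced disease, which would probably surface in disease-status, hospitalisation or adverse-event records in either arm.

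Much of this stands, and it rules out three stronger readings that a reader might infer:
- That examination is scheduled only in the ultrasound arm. Sections 7.5, 7.5.1 and 11.2.9 say otherwise, so the fault is a contradiction.
- That LND events will be under-detected. No detection rate is given, and under-detection depends on which sections sites follow. The six scans are not evidence of it either, because they are the intervention and are meant to find nodes before they become palpable.
- That the safety conclusion is compromised. The decision rule uses ultrasound-arm events only, and missed LND events would make ultrasound monitoring look worse, so they could not create a false claim of safety.

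The contradiction remains. No listed item names groin palpation for the LND arm from month 3 on, and the heading as worded permits remote collection of month-12 disease status. The blinded committee in section 12.5 reviews reported recurrences, so it cannot find one that nobody detected.

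**Conclusion.** The point holds as an internal contradiction about how the primary endpoint is ascertained in the LND arm, and it should be fixed. If the visit lists and schedule are followed, groin status may be collected differently in the two randomised arms. That exposes the per-group proportions and their difference, the answer on comparability, and the DFS comparison. The Bayesian safety rule, stopping boundaries and sample size are not affected.

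The size rests on the protocol's 3% and n=60: 1.8 expected events and 1.7 points for each one missed. As a yardstick, that is more than half of the 3-point gap between the anticipated 3% and the 6% limit (1.7/3 = 0.57). The spurious differences of 0.75 to 2.25 points assume detection of 75% down to 25% in the LND arm and full detection in the other. With so few events the comparison is imprecise in any case, which limits the consequence but does not remove the bias.

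**What to change.** Reconcile sections 7.5, 7.5.1 and 11.2.9 with sections 7.5.2, 7.5.4, 7.5.6, 7.5.8 and 16, so that one account of LND-arm visits and examinations stands throughout. Which clinical follow-up schedule is right is for the investigators.

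As outcome measurement, specify one 12-month groin-status assessment with the same method, window and eCRF item in both randomised arms. Record it at the month-12 visit that section 7.5 already describes, and exclude that item from the telephone/post option in section 7.5.8.

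The cost is small: protocol and eCRF wording, data entry, and in-person attendance at month 12 for this item. By section 7.5's own account LND women are already seen then. No sample size or error rate changes.

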8.1 EuroQoL-5D (EQ-5D)

The EQ-5D is one of the most frequently used generic, preference-based instruments for measuring the health utilities of patients in economic evaluations [37]. EQ-5D is a standardised instrument for use as a measure of health outcomes. It provides a descriptive profile and a single index value for health status. EQ-5D will measure changes in health status and quality of life to calculate the quality-adjusted life years (QALYs) gained with the intervention. The EQ-5D will be administered at baseline, 8 weeks, 6 months, and 12 months. This valid HRQL tool is also a utility measure in cost-effectiveness studies. For our short-term primary outcome, we will specifically focus on return to usual daily activities specified in the EQ-5D-5L with 5 levels (unable to do, severe-, moderate-, slight-, or no-restrictions), as consumers in our focus groups rated it as most relevant.

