3.2 Importance of Groin Nodes

Vulvar cancer develops from vulvar skin. It can spread locally to adjacent structures (vagina, urethra, anus) or via lymphatic channels to regional lymph nodes in the groin [2, 5]. If groin nodes are involved, the cancer is upgraded to Stage 3. This indicates a worse prognosis compared to tumours confined to local involvement [4]. Patients with groin node metastasis require further treatment. Unfortunately pre-treatment detection via groin clinical examination (palpation) and medical imaging scans do not reliably detect microscopic groin node involvement [2, 5]. Hence current clinical guidelines mandate that all patients (except those with Stage 1A disease) require surgical groin LND to mitigate the risk of missing groin node metastases [12]. In 30% of cases (~120 Australian women per year) a groin LND reveals positive (involved) nodes [8, 9], and a concomitant need for postoperative radiation treatment. Should positive groin nodes be missed and become enlarged and clinically palpable, more than 90% of patients will die within 12 months despite subsequent treatment [2, 5]. Conversely, if groin node involvement is detected early while still small, survival outcomes are expected to be excellent. For those reasons, the detection of clinically palpable, enlarged groin nodes is an appropriate marker for oncological safety in vulvar cancer (primary outcome of this clinical trial).

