5.6 Secondary Endpoint

1. HRQL and PROMS as measured by the EQ-5D and FACT-V at baseline, 8 weeks, 6 months, and 12 months
2. Morbidity at 12 months after surgery
3. Lower limb lymphoedema: incidence up to 12 months after surgery
4. Cost and cost effectiveness at 12 months post-surgery
5. Clinical accuracy of high-resolution ultrasound to predict groin lymph node involvement
6. Disease-free survival (DFS) and overall survival (OS)
7. Utility of biomarkers to reliably reflect the presence or absence of positive groin lymph nodes
8. Explore novel biomarkers for vulvar cancer

6. Study Design

A phase II, open label, multicentre, three-group, randomised clinical trial (ANVU).

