11.2.1 Incidence of Enlarged, Palpable Groin Nodes

Groin USM will be deemed acceptably safe if the probability that $P(\text{recur}|\text{USM}) < 0.06$ is 80% using the approach described [in section 11.1](#). This will be supplemented by conventional frequentist methods to estimate the proportion of women with clinically enlarged palpable groin node metastases at 12 months from randomisation for each group together with 95% confidence intervals. The difference in proportions between groups will also be calculated and presented with confidence intervals.

11.2.2 Impact of Ultrasound Surveillance on Quality of Life and Function, Pain, Lymphoedema and Morbidity

Demographics, behavioural characteristics and comorbidities will be captured at enrolment (baseline), 8 weeks, 6 months and 12 months, PROMs including HRQL and FoR (only at 12 months) will be assessed by a study-specific survey incorporating validated instruments:

PROMs will be scored according to their manuals to construct scales. Comparisons between randomised groups on PROMs scales will be performed using a linear mixed model for repeated measures accounting for stratification factors. Analysis will also be performed using a time-integrated approach to HRQL outcomes assessment pioneered by [name] [44]. Logistic regression will be used to compare groups on categorical outcomes (or an exact test if there are few events). Categorical outcomes include: return to usual activities at 8 weeks post-surgery; and the proportion of women experience a clinical relevant change in PROMs from baseline [45] at 8-weeks post-surgery, 6 months post-surgery, and 12 months post-surgery.

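### Section 8.1 labels EQ-5D-5L return to usual activities a primary outcome, contradicting the endpoint sections, where groin-node metastasis at 12 months is the sole primary

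*Protocol*

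**What the plan says.** **Section 8.1 (EQ-5D).** "For our short-term primary outcome, we will specifically focus on return to usual daily activities specified in the EQ-5D-5L". It lists the five response levels and explains that consumers in focus groups rated this item the most relevant. The EQ-5D is given at baseline, 8 weeks, 6 months and 12 months.

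**Where the primary is defined.** The synopsis gives it as "Incidence of clinically palpable, fixed to skin and histologically positive groin lymph nodes (node metastasis) at 12 months after surgical excision". Section 5.5 gives "Incidence of enlarged clinically palpable groin nodes (groin metastasis) in women randomised to serial high-resolution groin USM compared to surgical groin LND". Sections 3.2, 5.1 and 5.3 also name groin nodes only. These statements differ in the detail of the nodal definition, but none of them mentions the EQ-5D.

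**Where the EQ-5D is listed.** The first secondary endpoint in section 5.6 is "HRQL and PROMS as measured by the EQ-5D and FACT-V at baseline, 8 weeks, 6 months, and 12 months". The synopsis also lists it as secondary. Neither names the usual-activities item or singles out 8 weeks.

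**Analysis.** Section 11.2.2 says: "Categorical outcomes include: return to usual activities at 8 weeks post-surgery". These outcomes are compared between groups by logistic regression, or by an exact test if events are few. The only success criterion is in section 11.1 and is repeated in 11.2.1: an 80% posterior probability that recurrence under ultrasound monitoring (USM) is below 0.06.

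**The concern.** Which outcome is primary should be settled in one place and said the same way throughout. Here one item is primary in 8.1, an unnamed part of a secondary endpoint in 5.6, and a separate 8-week comparison in 11.2.2. Section 8.1 does not say how its primary outcome stands to the groin endpoint.

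The two outcomes may point in different directions. The protocol expects that sparing women a groin lymph node dissection (LND) will speed the return to normal activities (section 3.1). It also frames the choice as a trade-off against a potentially higher risk of nodal recurrence (section 8.5). Section 11.1 puts mortality after incurable groin recurrence above 90% within 12 months. For each woman the activity result comes 52 − 8 = 44 weeks, or about 10 months, before the safety result. An author relying on 8.1 could present a favourable 8-week comparison as a primary finding, whatever the recurrence rule shows. A later statistical analysis plan would inherit both statements.

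**Working it through.** **1. Does the activity item enter the design?** Start with the protocol's own figures in 11.1: true recurrence 3%, N = 120 under USM, 0.85 probability of declaring acceptable safety, less than 2% probability of stopping wrongly, and stopping boundaries 5/40, 6/60, 7/80, 9/100 and 10/120.

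- The model is Beta-Binomial: with prior Beta(a, b) and x events in n women, the posterior is Beta(a + x, b + n − x).
- The prior parameters are not stated, only that the prior is informed by 1/32. Two priors consistent with that, Beta(0.5, 15.5) and Beta(1.5, 31.5), both give exactly the stated boundaries under the 70% stopping rule.
- With either prior, the 80% rule is met at N = 120 with at most 5 events.
- Without interim looks, P(X ≤ 5) for X ~ Binomial(120, 0.03) is 0.847. Computed exactly over the five looks it is also 0.847. Stated: 0.85.
- The probability of crossing a stopping boundary at a true 3% is 0.018 (0.017 if the look at 120 is left out). Stated: below 0.02.

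Both figures reproduce from groin recurrence alone. No EQ-5D quantity enters them, so relabelling the item changes neither.

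**2. The statements side by side.**

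| Place | Status of groin nodes | Status of EQ-5D usual activities |
|---|---|---|
| Synopsis | Primary | EQ-5D secondary, item not named |
| 3.2, 5.1, 5.3, 5.5 | Primary | Not mentioned |
| 5.6 | – | EQ-5D secondary, item not named |
| 8.1 | Not mentioned | Short-term primary |
| 11.1, 11.2.1 | Sole success rule | Not mentioned |
| 11.2.2 | – | One categorical outcome, 8 weeks |

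Only 8.1 gives the item primary status. Only the groin endpoint has a criterion for success.

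**3. Can the item be met as a primary?** That would need a threshold, a significance level or a posterior rule. The protocol gives none, and gives no sample size or power for the item. There is therefore no defined event of the activity primary succeeding. What remains is a label attached to a comparison that will be made.

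**The case against.** The strongest reply is that this is one loose word. The groin endpoint is the sole primary wherever the primary is defined, the EQ-5D is listed as secondary, and 11.2.2 treats the item as one of several categorical patient-reported outcomes. Section 4 makes the next steps conditional on feasibility and safety. The synopsis deems the study complete only when 180 randomised women have finished 12 months, and no early 8-week readout is planned. Most of this stands, and it limits the point to a contradiction with a reporting risk. It does not remove the contradiction: 8.1 gives a reason for selecting the item, and 11.2.2 carries it into a between-arm comparison.

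A reader might go further and infer that the trial can succeed on a primary while failing its safety rule, or that two primaries inflate the error rate. The documents do not support this. The primary is judged by a posterior probability, so there is no alpha to split, and the activity item has no criterion. Even if one supposes an independent 5% test of the item, at a true recurrence of 6% the chance of at least one favourable result would be 1 − (1 − 0.267) × 0.95 = 0.304, against 0.267 for the safety rule alone. How often the two results would diverge depends on activity rates that the protocol does not give. With 120 against 60 women at two-sided 5%, power is about 0.49 for an assumed 65% against 50% and about 0.74 for 70% against 50%.

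A reader might also infer that the outcome will be cut to yes or no without regard to baseline. Section 11.2.2 does not define return, name a cut-off or exclude baseline, and the analysis plan may settle these matters.

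**Conclusion.** The contradiction is real and sits in operative outcome text: section 8.1 conflicts with the synopsis and with sections 3.2, 5.3, 5.5 and 5.6. Its consequence is limited to reporting, because the label leaves open which result may be presented as primary. There is no operative co-primary and no error-rate flaw. No design figure changes: 0.85 and less than 2% stand, as reproduced with at most 5/120 events for a safety declaration. That cut-off rests on priors inferred from the stated boundaries, but the conclusion here does not depend on the prior. The correction is worth making because it is cheap and settles the status of the 8-week result before any data are read. Baseline adjustment of that comparison is a free improvement and does not correct an error.

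**What to change.** 1. In 8.1, replace the primary label with *key short-term secondary outcome*.
2. In 5.6, name the item and time point: EQ-5D-5L usual-activities level at 8 weeks, compared between the randomised arms.
3. State once, in 5.5 or 5.6, that groin recurrence is the sole primary and that the 8-week result cannot by itself support replacing LND.
4. In 11.2.2, adjust the 8-week comparison for the baseline usual-activities level, which is already collected. An ordinal analysis of all five levels is optional.
5. If the sponsor does intend a co-primary, add it to 5.5 and 11.1 with a decision rule tied to the safety criterion.

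Items 1 to 4 need a wording amendment, with no new patients, visits or data. The downside is that the 8-week result can no longer be presented as a primary result. Item 5 would be a design change, with its own success rule to justify.
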